11.4. Appendix 4: Treatment Periods

For classifying AEs (including hypoglycemic events), the therapy periods will be defined as:

- **Pre-therapy:** The onset date of the AE is before the start date of randomized study medication. If the onset date of the AE is on the start date of randomized study medication, the AE will be considered as on-therapy.
- **On-therapy:** The onset date of the AE is on or after the start date of randomized study medication, and within last dose date plus 25 days in the albiglutide arm or within the last dose date in the lispro arm.
- **Post-therapy:** The onset date of the AE is more than 25 days after the last dose date in the albiglutide arm or after the last dose date in the lispro arm.

For immunogenicity data and other safety parameters that are assessed prior to administration of randomized study medication on dosing days, the therapy periods will be defined as:

- **Pre-therapy:** The assessment date is on or before the start date of randomized study medication.
- **On-therapy:** The assessment date is after the start date of randomized study medication, and within last dose date plus 25 days in the albiglutide arm or within the last dose date in the lispro arm.
- **Post-therapy:** The assessment date is more than 25 days after the last dose date in the albiglutide arm or after the last dose date in the lispro arm.

For an AE with an incomplete start date where the year and month are present while the day is missing, or where the year is present while both month and day are missing, the date is imputed in a dynamic way consistent with the partial date information so that the resulting AE therapy period assignment based on the imputed date is the most conservative possible, where the order from the most to the least conservative is: on-therapy phase > post-therapy phase > pre-therapy. Note that if the AE stop date is present, the imputed start date will always be on or prior to the stop date.

For the subjects in the insulin lispro + insulin glargine arm, the first drug dispense date recorded on eCRF after randomization is considered the starting date of treatment period. For the last dose date, it will be derived based on the last visit date. The last dose date will be Week 30 follow-up visit date for subject who completed the study, or the 4-week follow-up visit/end of study visit date for subjects who withdrew early.

For the subjects in the albiglutide + insulin glargine arm, the starting and last dose date will be derived based on the actual dose date of albiglutide in the exposure data set.

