5.7.1. Treatment Between Week 26 (End of Treatment)/Early Withdrawal and Follow-up

After completion of the end-of-treatment (Week 26) or early withdrawal visits, subjects will return to the study center in 4 weeks for the Follow-up visit. During this time, subjects will continue insulin glargine or insulin glargine plus insulin lispro to maintain adequate glycemic control.

For subjects in the albiglutide plus insulin glargine treatment arm, the last dose of once-weekly albiglutide will occur at Week 25. As needed, insulin lispro may also be re-introduced during this period according to the re-introduction of insulin lispro algorithm provided in Section 5.1.3.5. Insulin glargine alone (in subjects for whom insulin lispro has not been re-introduced) or insulin glargine and insulin lispro (in subjects for whom insulin lispro has been re-introduced) can be adjusted to achieve or maintain glycemic targets as close to normal as possible without untoward hypoglycemia

in accordance with product labeling in the respective country and standards of care at the study center.

For subjects in the insulin glargine plus insulin lispro treatment arm, both insulin glargine and insulin lispro may be adjusted to achieve or maintain glycemic targets as close to normal as possible without untoward hypoglycemia in accordance with product labeling in the respective country and standards of care at the study center.

Note: During this time, subjects must not use any prohibited medications or nondrug therapies (see Section [5.6.2](#)).

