5.6. Multiple Evaluations

After all the records have been slotted based on therapy period and study day, if there are multiple valid records for an assessment within an assigned analysis visit, only one of these records will be used for summary statistics and analyses. The record to be used is determined using the following hierarchy (in decreasing order of priority):

- the record closest to the target visit day
- the record with an original nominal visit that matches the analysis visit
- the record earliest in time for postbaseline assessments; for baseline, it is the record latest in time

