6.5. Exposure to Study Drug

Descriptive statistics including the number of subjects, mean, standard deviation, median, minimum, and maximum for the duration of study drug exposure to the treatment received will be presented by treatment group for the Safety Population. The duration of study drug exposure is defined as date of last dose of randomized study drug - date of first dose of randomized study drug + 1. The total person time on treatment (in years) as defined in [Appendix 5](#) will also be displayed for each treatment group.

Additionally, the prescribed total daily dose of insulin glargine and insulin lispro will be tabulated by visit.

A by-subject listing of study drug administration will also be presented.

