8.3.2. Adverse Events

All AEs will be coded using MedDRA which will be updated whenever available throughout the life of the study. Adverse events will be categorized by their occurrence in regard to therapeutic phase (pre-therapy, on-therapy, or post-therapy) as defined in [Appendix 4](#). Adverse events will be summarized in various subsets by treatment group. An overview summary of the number and percentage of subjects with any AE, the total number of AEs recorded, and the overall AE density and incidence rate for on-therapy AEs will be provided by treatment group. The overview will also summarize SAEs, treatment-related AEs, AEs by maximum intensity, and AEs by therapy phase.

Summaries of the number and percentage of subjects with any treatment-emergent AEs (TEAEs), related AEs, AEs leading to treatment discontinuation or withdrawal from study, SAEs, fatal AEs etc, will be provided. Adverse events will also be summarized by maximum intensity (mild, moderate, and severe).

Except summaries for serious AEs, AEs leading to withdrawal from treatment or pre-therapy AEs, all other AE summaries do not include hypoglycemic events, unless otherwise specified.

All AEs will be listed in a subject data listing.

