11.3.2. Visit Slotting Algorithm

For all safety and efficacy parameters to be summarized or analyzed by visit, data records will be slotted to one of the protocol specified visits using the following algorithm:

- a) Determine the therapy period and study day for all records using the algorithms from Appendix 4: Treatment Periods.
- b) For all records (including unscheduled visit records, early withdrawal records and repeat visit records), use the therapy period and study day determined above with the slotting intervals in the Table Analysis Visit Windows below to slot the record to the appropriate analysis visit.
 - For records determined to be in the pre-therapy period, the Week -6 and Week -4 analysis visits will be based on the nominal visits recorded on the eCRF. The Week -1 and Baseline analysis visits will be assigned based on the study day slotting intervals as shown in the table below.
 - For records determined to be in the on-therapy period, use the study day with the slotting intervals in the table below to assign the records to the appropriate on-therapy analysis visit (Week 1 through Week 26).
 - For records determined to be in the post-therapy period, the study day will not be used for assigning the analysis visit. Instead, all post-therapy period records for subjects who complete randomized study treatment according to protocol will be assigned to the Week 30 post-therapy analysis visit. For subjects who terminate study treatment early, the follow-up analysis visit will be based on the nominal visit recorded on the eCRF. All other post-therapy period records for subjects who terminate study treatment early will be assigned to the 4 Week Follow-up analysis visit.

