11.3.4. Analysis Visit Windows

Table - Analysis Visit Windows

Scheduled Visit	Target Study Day of Visit	Slotting Intervals
Week -6	-42	Visit = " SCREENING"
Week -4	-28	Visit = " STANDARDIZATION 1"
Week -1	-7	Visit = " STANDARDIZATION 4"
Baseline (Week 0)	1	Visit = " BASELINE"
Week 4	29	2 to 32 days
Week 5	36	33 to 53 days
Week 10	71	54 to 99 days
Week 18	127	100 to 155 days
Week 26 (End of Treatment Visit)*	183	Albiglutide arm: 156 to (last dose date + 25 days) Lispro arm: 156 to last dose date
Week 30**	211	For subjects completed study Albiglutide arm: >Last dose date + 25 days Lispro arm: >Last dose date
4 Week Follow-up Visit**	Last dose date + 35 days***	For subjects didn't complete study Albiglutide arm: >Last dose date + 25 days Lispro arm: >Last dose date

* Week 26 is the end of treatment visit for those subjects completing the study per-protocol. For subjects who withdraw early from active treatment, the end of treatment visit will be assigned to an analysis visit based on the visit slotting algorithm using study day and therapy phase.

** Week 30 is the 4 week post-treatment follow-up visit for those subjects completing the study per-protocol. The 4 Week Follow-up Visit is the 4 week post-treatment follow-up visit for those subjects who withdraw early from active treatment. Both visits will be assigned based on the visit slotting algorithm using therapy phase.

*** The target study day for the 4 Week Follow-up Visit for subjects who withdraw early from active treatment is set to be 5 weeks (35 days) after last dose to correspond with the timing of the 4 week post-treatment follow-up for subjects completing the study per-protocol (where last dose is at Week 25 and the follow-up visit is at Week 30).

For parameters which were not scheduled to be collected at all visits, the all-inclusive visit intervals defined for all visits (that is, the visit window table above) will still be used to slot records. However, if a value is slotted to a visit unscheduled for a parameter, it will not be summarized (and not be included in the efficacy datasets) but will be included in data listings.

For analyses on the prescribed insulin dose, the total number of weekly insulin injections and SMBG profile, visit and visit dates recorded on the eCRF are used for analysis because a specific visit date is needed to calculate the analysis values.

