11.5.3. Total Person Time on Treatment

The total person time on albiglutide treatment (in years) is defined as the total time on study medication between the time of the last dose date and the first dose date plus 26 days (to account for the long half-life of albiglutide) day and then divided by 365.25 days/year. For insulin lispro, it defined as the duration of study drug exposure (defined as the total time between the last dispensed dose date of randomized treatment and the first dose date of randomized treatment plus 1 day) divided by 365.25 days/year.

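### The SAP gives the lispro arm conflicting end dates: read literally, its on-therapy event rates are inflated by about 15%, and some lispro follow-up weights are analysed as Week 26.

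*SAP*

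**What the plan says.** **Event window.** SAP 11.4 counts a lispro-arm event as on-therapy up to the last dose date. That date is derived from visits: "The last dose date will be Week 30 follow-up visit date for subject who completed the study", and the 4-week follow-up or end-of-study visit for early withdrawals.

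**Person-time.** SAP 11.5.3 calls lispro person-time the duration of study drug exposure and measures it as "total time between the last dispensed dose date of randomized treatment and the first dose date of randomized treatment plus 1 day". SAP 11.5.4 uses this as the denominator of every AE density and incidence rate. SAP 6.5 defines the same term differently: "duration of study drug exposure is defined as date of last dose of randomized study drug", minus the first dose date, plus 1.

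**Dispensing.** The study-visit schedule (Protocol Table 5, repeated in SAP 11.2.1) has its last dispensing at Week 26 or Early Withdrawal and none at follow-up.

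**Visit slots.** In SAP 11.3.4 the Week 26 slot is "Lispro arm: 156 to last dose date", and the Week 30 and 4-Week Follow-up slots take only lispro records after the last dose date. SAP 11.3.2 exempts a record from study-day slotting only when it is post-therapy: "For records determined to be in the post-therapy period, the study day will not be used for assigning the analysis visit". When several records share a slot, SAP 5.6 gives first priority to "the record closest to the target visit day".

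**Use.** SAP 8.3.2 plans the "overall AE density and incidence rate for on-therapy AEs" by treatment group, and SAP 8.3.5.1 plans the same rates for hypoglycemia.

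**The concern.** Two things go wrong if these sections are programmed as written.

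First, the lispro rate numerator runs to the follow-up visit while its denominator can stop four weeks earlier. The albiglutide arm has no such gap. Any on-therapy rate not cut off at Week 26 is then overstated for the comparator only. For hypoglycemia that favours the result the SAP synopsis says it expects, namely less of it on albiglutide.

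Second, the lispro last dose date is itself the follow-up visit date, so a scheduled lispro record cannot fall after it. The lispro post-therapy period and both lispro follow-up slots are empty apart from rare late safety samples. Follow-up weights are then on-therapy records and are slotted by study day. From Day 156 onward that means Week 26. Change in body weight at Week 26 is a formally tested key secondary endpoint (SAP 11.10), and the matching albiglutide record is generally post-therapy and kept out.

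**Working it through.** **Inputs.** Target days come from SAP 11.3.4, the albiglutide rules from 11.4 and 11.5.3, and the 15% withdrawal from SAP 11.12 (337 completers and 60 withdrawals of 397 per arm).

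**1. Reproduce the plan's days.** Target day = 7 × week + 1 gives Week 18 = 127, Week 26 = 183 and Week 30 = 211, as stated in 11.3.4. The last albiglutide dose at Week 25 is Day 176, and 176 + 35 = 211 agrees with the table footnote.

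**2. Albiglutide completer.** The window ends at 176 + 25 = Day 201. Person-time is 176 − 1 + 26 = 201 days. Ratio 201/201 = 1.00.

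**3. Lispro completer.** The window is 211 days. Inflation = window ÷ person-time, assuming a constant event rate.

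| Reading of the 11.5.3 end date | Person-time (days) | Ratio |
|---|---|---|
| Same as the 11.4 last dose date (consistent with 6.5) | 211 | 1.000 |
| Last scheduled dispensing, Week 26 | 183 | 1.153 |
| Last dispensing at Week 18 (off schedule) | 127 | 1.661 |

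On the Week 26 reading, a true rate of 100 per 100 person-years in both arms is reported as 115.3 for lispro. If the event rate after Week 26 is 0.5 to 1.25 times the earlier rate (assumed), (183 + 28r)/183 runs from 1.08 to 1.19.

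**4. Lispro early withdrawal on Day d**, with dispensing at that visit and follow-up 28 days later: ratio (d + 28)/d. Day 71 gives 1.394 and Day 127 gives 1.220.

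**5. Whole lispro arm**, mean withdrawal day m (assumed): (337 × 211 + 60(m + 28)) / (337 × 183 + 60m).

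- m = 45: 75,487/64,371 = 1.173
- m = 91.5: 78,277/67,161 = 1.166
- m = 137: 81,007/69,891 = 1.159

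**6. Weights.** Follow-up on Day d + 28 reaches the Week 26 slot when d ≥ 128.

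- For d = 128 to 155, the end-of-treatment weight falls in the Week 18 slot (Days 100 to 155), so the follow-up weight is the scheduled one in the Week 26 slot.
- For d ≥ 156, both weights are in the Week 26 slot. Follow-up is closer to Day 183 when (d + 28) − 183 < 183 − d, that is d < 169.

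Days 128 to 168 are 41 days. If 60 withdrawals are spread evenly over 182 days (assumed), 60 × 41/182 = 13.5 lispro subjects are affected, or about 7 at half that density. Their share of Week 26 weights is 13.5/(337 + 13.5) = 0.039, or about 0.020 at half density. Each 1 kg of deviation in those weights therefore moves the lispro mean by about 0.02 to 0.04 kg.

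For albiglutide on the same dates, the on-therapy window ends no later than d + 25, before d + 28, so the record is post-therapy.

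Completers are protected by the closest-record rule. Their Day 211 weight is used only if no other weight is in the slot.

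**The case against.** The strongest reply is that the inflation may be zero. SAP 6.5 names no lispro date. Combined with 11.4 it gives 211 days, and the 11.5.3 wording could mean the last dose of dispensed drug. Protocol 5.7.1 supports a Week 30 end: "During this time, subjects will continue insulin glargine or insulin glargine plus insulin lispro to maintain adequate glycemic control". This reading is possible, and the true conflict is 11.5.3 against 11.4, with 6.5 on the side of 11.4. But the dispensing reading is not strained: 11.4 itself starts the lispro period at the first dispense date. Continued insulin use justifies a Week 30 numerator, not a shorter denominator. Nothing in the SAP settles which date is meant.

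It is also fair that the consequences are limited. The protocol (8.3.5.2) plans no inferential testing of safety variables. The Poisson comparison in 8.3.5.1 follows counts in intervals that end at Week 26. The titles of Tables 3.76 to 3.79 state no such cut, so an effect there is possible but not shown. The overall on-therapy rates in 8.3.2 and 8.3.5.1 have no stated cut and are exposed. The 66% figure needs an off-schedule last dispensing and only marks the outer bound.

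On weights, the contrast between arms is less clean than the arithmetic. Visits after Week 16 may move by 7 days, so some albiglutide follow-up weights can fall within 25 days of the last dose and also count as on-therapy. The effect is small against the 1.5 to 2.6 kg differences the protocol cites from earlier studies. The sentence in 11.3.2 that assigns early withdrawals' follow-up by nominal visit does not help, because it sits under the rule for post-therapy records.

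**Conclusion.** The concern holds. As written, 11.4 and 11.5.3 give lispro an event window and a person-time that need not match, and 6.5 and 11.5.3 define one term in two ways. On the literal reading, on-therapy lispro rates are overstated by 15.3% for an on-schedule completer and by about 16% to 17% for the arm. This assumes a constant event rate, last dispensing at Week 26 or at withdrawal, and 60 withdrawals. The alternative reading gives 0%. Two competent programmers could therefore report different lispro rates from the same data.

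The slot problem is real but small: about 7 to 14 of 397 lispro subjects under the stated assumptions.

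Not shown to be affected are the primary HbA1c endpoint (not sampled at follow-up), the percentage of subjects with hypoglycemia through Week 26, and interval counts stopped at Week 26. This should be fixed before analysis; it does not threaten the primary conclusion.

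**What to change.** 1. Define one lispro end date and use it in SAP 6.5, 11.3.4, 11.4 and 11.5.3.
2. Define person-time in each arm as exactly the window over which events are counted. Week 30 is acceptable for lispro AEs provided lispro person-time also runs to Week 30.
3. Separately, close the lispro Week 26 efficacy slot at the Week 26 or end-of-treatment visit, and send follow-up visit records to the follow-up slot in both arms.
4. SAP 11.3.3 applies its 14-day rule to the last dose date recorded on the CRF. State how that date relates to the derived lispro date in 11.4.

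The cost is SAP wording and a change to a derived date in programming, with no new data. Reported lispro rates will be lower than under the literal reading, and a few late-withdrawal lispro subjects will lose a Week 26 weight.

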11.5. Appendix 5: Derived and Transformed Data

11.5.1. Change from Baseline

The baseline value for an assessment is defined as the last available non-missing value prior to the first dose of the randomized treatment. Change from Baseline is defined as the postbaseline value minus the baseline value for the given assessment.

11.5.2. Body Mass Index Calculation

Body mass index (BMI) will be calculated as follows:

$$\text{BMI} = \frac{\text{weight (kg)}}{[\text{height (m)}]^2}$$

11.5.3. Total Person Time on Treatment

The total person time on albiglutide treatment (in years) is defined as the total time on study medication between the time of the last dose date and the first dose date plus 26 days (to account for the long half-life of albiglutide) day and then divided by 365.25 days/year. For insulin lispro, it defined as the duration of study drug exposure (defined as the total time between the last dispensed dose date of randomized treatment and the first dose date of randomized treatment plus 1 day) divided by 365.25 days/year.

11.5.4. AE (Event) Density and Incidence Rate

AE density, also referred to as event density, will be calculated as the number of events in a given period divided by the total person time on treatment (in years) of subjects at risk at the beginning of the same period. The incidence rate for an AE will be calculated as the number of subjects experiencing that AE within a given period divided by the total person time on treatment (in years) of subjects at risk at the beginning of the same period.

To enhance the data presentation and to aid comparison between treatment groupings, all AE densities and all incidence rates of AEs will be presented per 100 person-years (by multiplying the above defined statistics by 100).

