8.3.3.2. Other Comparisons of Interest

A key secondary endpoint is the proportion of subjects treated with once-weekly albiglutide that are able to replace prandial insulin without the need for re-introduction of insulin lispro. The 95% confidence interval of the sample proportion will be estimated, stratified by region, age category, and current use of metformin.

The proportion of subjects with hypoglycemia, as confirmed by plasma glucose monitoring <70 mg/dL (<3.9 mmol/L) and/or requiring third-party intervention through Week 26, will be compared between treatment groups, adjusting for baseline HbA_{1c} stratum, age group, current use of metformin, and region.

Other binary secondary endpoints, such as the proportion of subjects achieving HbA_{1c} treatment goals at Week 26 and the proportion of subjects achieving composite secondary endpoints (i.e., criteria involving HbA_{1c} target and hypoglycemia) will be analyzed analogous to the proportion of subjects with hypoglycemia.

Continuous secondary endpoints, e.g., changes over time in HbA_{1c}, FPG, and body weight, changes in daily insulin dose, changes in mean daily blood glucose based on 8-point SMBG, and changes in total number of weekly insulin injections will be summarized descriptively and analyzed using an MMRM (observed data). In the MMRM for non-HbA_{1c} endpoints, the corresponding baseline variable will be modeled as a covariate (in place of baseline HbA_{1c}) for variance reduction and to adjust for any baseline differences in treatment groups attributable to chance as well as the randomization stratification variables (HbA_{1c} stratum, age category, current use of metformin).

The number of hypoglycemic events with confirmed home blood glucose monitoring <70 mg/dL (<3.9 mmol/L) and/or requiring third-party intervention in 3-month intervals (i.e., from Baseline/Randomization to Week 12, >Week 12 to Week 26) will be compared between the treatment groups using a Poisson regression model with offset for the person-year, which will include treatment effect and covariates such as HbA_{1c} stratum, age (<65 years versus ≥65 years), current use of metformin (metformin use versus no metformin use), and region.

The time to meeting prespecified criteria for severe, persistent hyperglycemia at Week 26 will be analyzed for treatment group differences using pairwise log-rank tests within a Kaplan-Meier model.

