8.3.5. Adverse Events of Special Interest

For selected AEs of special interest such as hypoglycemia, the exposure-adjusted event rate, i.e., AE density, will be calculated as the number of events in a given period divided by the total person time on treatment of subjects at risk within the same period; the exposure-adjusted incidence rate will also be calculated as the number of subjects in a given period divided by the total person time on treatment of subjects at risk within the same period. The exposure-adjusted event rate and incidence rate will be expressed as an annualized rate (expected number of events or subjects per 100 person-years).

For any AEs of special interest, if the number of events is limited and does not warrant summary tables, by subject data listings will be provided instead.

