8.3.5.1. Hypoglycemic Events

Hypoglycemic events merit special attention in the development and study of drugs for the treatment of T2DM since they are often related to the efficacy of a compound. In order to accomplish this, hypoglycemic event data including supplemental hypoglycemic event information not collected on AE eCRF page are reported on a separate hypoglycemic event eCRF page. However, any hypoglycemic event that meets the criteria for a serious AE will also be included in the serious AE summaries.

Analysis of on-therapy hypoglycemic events will include all AEs coded to the preferred term of 'Hypoglycemia'. For on-therapy hypoglycemic events the number and percentage of subjects with events, the number of events, the incidence rate (per 100 person-years) and AE density (per 100 person-years) by the severity of the event defined by American Diabetes Association [ADA], SAE status, relationship to the investigational product, and withdrawal status will be summarized by treatment group. The events will also be summarized according to intervention provided, action taken with regard to background and anti-hyperglycemic medications and onset week and glucose levels. All hypoglycemic events will be classified as severe, documented symptomatic,

asymptomatic, probable symptomatic, or pseudohypoglycemia per the American Diabetes Association criteria) criteria.

The number of events of hypoglycemia with confirmed home blood glucose monitoring < 3.9 mmol/L and/or requiring third party intervention (i.e., severe, documented symptomatic and asymptomatic hypoglycemic events) in 3 monthly intervals (i.e., from Baseline to Week 12, >Week 12 to Week 26) will be summarized by treatment group. The exposure-adjusted event rate will be compared between treatment groups using a Poisson regression model with offset for the person-year, which will include HbA_{1c} stratum, age (<65 years versus ≥65 years), current use of metformin (metformin use versus no metformin use), and region as covariates.

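### SAP 11.5.4 read with 11.5.3 puts whole-treatment person-time under interval hypoglycemia counts; programmed as written, the absolute 3-month rates would be roughly halved

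*SAP*

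**What the plan says.** SAP 8.3.5.1 summarizes the number of confirmed hypoglycemic events "in 3 monthly intervals (i.e., from Baseline to Week 12, >Week 12 to Week 26". Its next sentence says that the exposure-adjusted event rate is compared between arms by Poisson regression with a person-year offset. Protocol 8.3.3.2 makes the link explicit: the event counts in 3-month intervals "will be compared between the treatment groups using a Poisson regression model with offset for the person-year". The list of departures from the protocol in SAP 2.1 does not withdraw this.

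Two places in the SAP define the rate.

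- SAP 11.5.4, the derivation appendix, takes the events of one period, "divided by the total person time on treatment (in years) of subjects at risk at the beginning of the same period".
- SAP 8.3.5, which names hypoglycemia, takes them "divided by the total person time on treatment of subjects at risk within the same period". Protocol 8.3.5.2 uses the same formula.

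The person-time is defined once, in SAP 11.5.3. For albiglutide it is "the total time on study medication between the time of the last dose date and the first dose date plus 26 days". For lispro it is the time between "the last dispensed dose date of randomized treatment and the first dose date of randomized treatment plus 1 day". Neither definition has an interval version.

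SAP 11.4 gives a different lispro end date: "The last dose date will be Week 30 follow-up visit date for subject who completed the study". The example Poisson code in SAP 11.11.1 uses an offset called PYOFFSET and does not say how it is derived.

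**The concern.** In 11.5.4 the reference to the start of the period selects which subjects contribute. It does not limit the days that each one contributes. A programmer who follows 11.5.4 and then looks up the person-time in 11.5.3 would put a subject's full treatment time under events from only 12 or 14 weeks. Both interval rates would then be too low. Every interval would share nearly the same denominator, so the rates would not be rates for those intervals at all.

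Less hypoglycemia is one of the benefits that the protocol expects from replacing prandial insulin with albiglutide. The interval rates would show how hypoglycemia changes over the treatment period. A reader comparing them with the overall rate, or with another trial, would be misled.

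**Working it through.** The documents state no hypoglycemia rate, so there is no planned figure to reproduce.

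**Inputs**

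- Interval lengths (SAP 8.3.5.1): 12 × 7 = 84 days and 14 × 7 = 98 days.
- Albiglutide completer: first dose Day 1, last dose at Week 25 (protocol Table 5, footnote 4), taken as Day 176. By 11.5.3, person-time is 176 − 1 + 26 = 201 days.
- Lispro completer by 11.5.3: protocol Table 5 schedules dispensing at Week 26 (target Day 183), so person-time is 183 − 1 + 1 = 183 days.
- Lispro completer if the last dose date follows 11.4: Week 30 visit (target Day 211), so 211 − 1 + 1 = 211 days.
- Assumption: a constant event rate over time.

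**Formula.** The reported rate divided by the true interval rate equals interval days divided by person-days in the denominator.

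| Completer | Denominator | Baseline to Week 12 | Week 12 to Week 26 |
|---|---|---|---|
| Albiglutide | 201 days | 84/201 = 0.42 | 98/201 = 0.49 |
| Lispro, last dispensing at Week 26 | 183 days | 84/183 = 0.46 | 98/183 = 0.54 |
| Lispro, Week 30 rule | 211 days | 84/211 = 0.40 | 98/211 = 0.46 |

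For an assumed true rate of 500 per 100 person-years, albiglutide would show 500 × 84/201 = 209 in the first interval and 500 × 98/201 = 244 in the second.

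**With withdrawals.** The design assumes 15% early withdrawal. Spreading this uniformly over 26 weeks (an assumption) and simulating gives 0.44 and 0.48 for albiglutide. Lispro gives 0.48 and 0.53 under the Week 26 rule, or 0.42 and 0.46 under the Week 30 rule. The size is essentially unchanged.

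**Effect on the albiglutide-to-lispro rate ratio.** The interval length cancels, which leaves lispro person-time divided by albiglutide person-time:

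- 183/201 = 0.91, so the ratio is about 9% too low;
- 211/201 = 1.05, so the ratio is about 5% too high.

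A less likely case is that the Week 26 supply is not counted as dispensing of randomized treatment. The last dispensing would then be at Week 18 (127 days), lispro would show 0.66 and 0.77, and the factor would be 127/201 = 0.63.

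**With person-time limited to the interval.** Completer denominators become 84/365.25 = 0.230 years and 98/365.25 = 0.268 years. As written they are 201/365.25 = 0.550 years (albiglutide) and 183/365.25 = 0.501 years (lispro) in both intervals. The ratio to the true rate returns to 1.00.

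**The case against.** The strongest reply is that 11.5.4 is a general definition, and that the interval problem does not arise when the period is the whole on-therapy phase. For hypoglycemia, SAP 8.3.5 and protocol 8.3.5.2 place the person-time within the same period, which can naturally be read as interval time. SAP 8.3.5.1 promises interval counts outright but does not say outright that the rate is computed per interval. Table 3.75 is titled by interval, whereas the titles of rate Tables 3.76 to 3.79 name none. PYOFFSET is undefined, and the example code has a repeated-subject statement, so the offset could be specific to each interval record.

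Much of this stands. It means that the documents do not establish what would be programmed. It does not remove the conflict. The wording in 8.3.5 can equally attach to the subjects at risk, it relies on the same whole-treatment term, and 11.5.4 is where a programmer looks for the derivation. Protocol 8.3.3.2 also ties the Poisson comparison to the 3-month counts.

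A reader might infer that the comparison is biased in favor of albiglutide because its person-time carries an extra tail after the last dose. The documents do not support a direction: the factor is 0.91 or 1.05 according to which lispro end date is used.

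A reader might also infer that splitting person-time at Week 12 would still leave the second albiglutide interval about 16% too low (98/117 = 0.84, with 201 − 84 = 117). That figure assumes that events stop counting at Day 182, and SAP 8.3.5.1 sets no such day. Day 182 appears in SAP 8.1.3.5, for the hyperglycemia analysis. On-therapy albiglutide events run to 25 days after the last dose (SAP 11.4), so numerator and denominator could match.

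**Conclusion.** The point holds as a conflict between stated rules, one of which gives a wrong interval rate. Followed literally, 11.5.4 with 11.5.3 would report absolute 3-month rates at about 0.40 to 0.54 of their true values for completers, assuming a constant event rate and lispro person-time of 183 or 211 days. It would be too strong to say that the trial's interval rates will come out halved, because 8.3.5 and protocol 8.3.5.2 allow the correct reading and the offset is undefined.

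The between-arm ratio is much less affected under either of those lispro end dates, and its direction is unresolved. The key secondary hypoglycemia endpoint is a percentage of subjects tested by Cochran-Mantel-Haenszel (SAP 8.1.2.2) and uses no person-time. The Poisson comparison lies outside the confirmatory test sequence (SAP 5.1 and 11.10). The consequence is therefore limited to the supportive rates, but it is worth correcting before programming.

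**What to change.** 1. In SAP 11.5.4 and 8.3.5.1, define person-time for an interval as the subject's on-therapy days that fall inside that interval.
2. In SAP 11.11.1, define PYOFFSET as the log of that quantity, in years, and say whether each subject contributes one record or one per interval.
3. State one end day for the second interval, and apply it to both events and person-time in both arms.
4. Give SAP 8.3.5 and 11.5.4 the same wording for the denominator.
5. Reconcile the lispro end date in 11.5.3 (last dispensing) with that in 11.4 (Week 30 visit for completers).

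The cost is SAP wording and one derived variable. No new data are needed.
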